9.9. Study Size

9.9.1. Sample Size

Table 9.4 presents by outcome the sample size (number of live births or pregnant individuals, depending on the outcome) required in each cohort to detect a range of relative risks, from 1.5 to 5.5. Sample size calculations were performed with SAS® statistical software (version 9.4 or higher, SAS Institute, Cary, NC) for the outcomes using the Fisher's exact conditional test with Walters normal approximation method, and assuming a power of 80%, a 2-sided α level of 0.05, an equal number of individuals in each cohort (although other sampling ratios were considered), and observed prevalence of the outcomes in the comparator cohort equivalent to reference rates in the general population. These general population rates were obtained for most (but not all) of the outcomes from various sources, including the Metropolitan Atlanta Congenital Defects Program (MACDP), the National Vital Statistics System (NVSS), and published literature.

Although the registry aims to examine a variety of maternal, fetal, and infant outcomes, the target sample size for the registry is based on the primary outcome, overall prevalence of MCM, which also is the outcome with the most restrictive denominators and one of the lowest prevalence in the general population.

As shown in Table 9.4, 265 live births in the analysis population of each cohort are needed to detect a 3-fold increase in the overall prevalence of MCM between cohorts, or a relative risk of 3.

To estimate the number of pregnant individuals who will need to be enrolled to result in 265 live births per cohort, several factors were considered, including the expected registry live birth rate, the proportion of enrolled individuals expected to be exposed to tirzepatide in the first trimester, and the proportion of enrolled individuals expected to be excluded from the analysis population. It was assumed that 90% of enrolled individuals would be exposed in the first trimester, 90% of enrolled pregnancies would result in a live birth,^{72,73} and 10% of enrolled individuals would be excluded from the analysis population due to the occurrence of pregnancy outcome prior to enrollment (retrospectively enrolled participants), exposure to a known teratogen or an investigational medication or congenital infectious agents during pregnancy (teratogen/investigational medication/congenital infectious agent-exposed participants), lack of pregnancy outcome data (participants lost to follow-up; assumed to constitute 5%), or inclusion of a prior pregnancy in the analysis population (subsequent pregnancies). These assumptions are based on experience with other similar study designs. To ensure adequate sample size in the main analysis population is achieved, enrollment of the main analysis population will be assessed throughout data collection. If higher than anticipated percentages of participants would be excluded from the analysis population, it will be assessed what (if any) potential mitigations should be implemented. It is also acknowledged that there could be some effective sample size loss due to the use of stabilized IPTW. The extent and potential mitigations for this will be assessed after approximately 100 participants have enrolled in each of the cohorts.

Given these assumptions, to attain 265 live births per cohort, 364 (=265/0.9/0.9/0.9) pregnant individuals would need to be enrolled in each of the three cohorts of the study population, and a

total of 1,092 individuals would need to be enrolled in the registry. This sample size will afford the study the ability to detect a 3-fold increase in the overall prevalence of the primary outcome, MCM, in the tirzepatide-exposed cohort, with meaningful confidence (95% confidence level). Additionally, [Table 9.5](#) shows that, without any adjustments for multiple comparisons, the proposed sample size will also afford the study >80% power to detect a 3-fold increase in several of the secondary and exploratory outcomes.

The overall prevalence of MCM is higher among individuals with obesity (BMI >30 kg/m²; 3.9%²⁶) than that of the general population (3%).⁷⁴ However, because it is difficult to estimate the proportion of enrolled individuals who will have obesity at the time of conception (as some will have lost weight prior to conception due to weight management treatment), the more conservative approach assuming an overall prevalence of 3% has been chosen (i.e., the overall sample size calculations were based on the general population prevalence of MCM). Had the higher rate (3.9%) been used, the total sample size for the registry would have been substantially lower (828 vs. 1092). These assumptions also may be re-evaluated after interim analyses have been conducted.

Table 9.4. Sample Size Needed per Cohort to Detect Specific Relative Risk (Exposed: Tirzepatide Unexposed^c)

Outcomes ^a	Reference Prevalence in Unexposed Group	Reference	Denominator of Reference	RR= 1.5	RR= 2.0	RR= 2.5	RR= 3.0	RR= 3.5	RR= 4.0	RR= 4.5	RR= 5.0	RR= 5.5
Primary Objective												
MCM	3.0%	CDC 2008 ⁷⁴	Live births	2,627	796	413	265	190	146	117	97	82
Secondary Objectives												
Pre-eclampsia	3.8%	Ananth 2013 ⁷⁵	Pregnant individuals	2054	622	322	206	148	113	91	75	64
Eclampsia	0.281%	Butwick 2020 ⁷⁶	Live births	28973	8824	4600	2961	2130	1640	1322	1101	940
Gestational diabetes	6.9%	Martin 2021 ⁷⁷	Pregnant individuals	1161	350	180	115	82	62	50	41	35
Pregnancy-induced hypertension	6.5%	Butwick 2020 ⁷⁶	Pregnant individuals	1088	327	169	107	76	58	46	38	32
SAB	11.8%	Wu 2019 ⁷⁸	Pregnant individuals	596	177	90	57	40	30	24	19	16
Stillbirth	0.596%	MacDorman 2015 ⁷⁹	Live births and stillbirths	13610	4142	2159	1389	999	769	619	516	440
Induced abortion	18.6%	Jatlaoui 2019 ⁸⁰	Live births	343	100	50	31	21	15	12	9	NA ^b
Preterm birth	8.47%	Martin 2021 ⁷⁷	Singleton live births	868	260	134	85	60	46	36	30	25
SGA	10.0%	By definition	Live births	721	215	110	70	49	37	29	24	20
Postnatal growth deficiency	10.0%	By definition	Live births	721	215	110	70	49	37	29	24	20
Infant developmental delay	13%	Rosenberg 2008 ⁸¹	Live births	532	158	80	50	35	26	21	17	14
Exploratory Objectives												
Heart Failure	0.12%	Mogos 2018 ⁸²	Pregnant individuals	667975	20706	10798	6952	5002	3853	3107	2588	2210

Outcomes ^a	Reference Prevalence in Unexposed Group	Reference	Denominator of Reference	RR= 1.5	RR= 2.0	RR= 2.5	RR= 3.0	RR= 3.5	RR= 4.0	RR= 4.5	RR= 5.0	RR= 5.5
Peripartum Cardiomyopathy	0.03%	Harper 2012 ⁸³	Live births	272189	82925	43251	27847	20039	15437	12450	10374	8858
Hyperemesis gravidarum	2.5% (0.3 to 3.5%)	ACOG 2015 ⁸⁴	Pregnant individuals	3171	962	500	321	230	176	142	118	100
Inadequate GWG	15% (12 to 25%)	CDC 2015 ⁸⁵	Pregnant individuals	448	132	67	42	29	22	17	13	11
LGA	10.0%	Hocquette 2021 ⁸⁶	Live births	721	215	110	70	49	37	29	24	20
Rapid infant weight gain	8% (5 to 14%)	Eckhardt 2016 ⁸⁷	Live births	925	278	143	91	64	49	39	32	27

Abbreviations: GWG = gestational weight gain; MCM = major congenital malformation; NA = not available; reference prevalence = prevalence of outcome in general population for pregnant individuals of any age; RR = relative risk; SAB = spontaneous abortion; SGA = small for gestational age.

^a Only outcomes with published reference rates in the general population are included in the table.

^b For induced abortion, an RR of 5.5 with a reference rate of 18.6% in the unexposed cohort would result in a rate above 100% in the exposed cohort.

^c Sampling ratio is 1:1 (Exposed: Tirzepatide Unexposed). Comparisons between tirzepatide exposed vs. AOM active comparator and tirzepatide exposed vs. AOM unexposed comparator will be conducted separately.

Notes: Sample size calculations were performed in SAS (version 9.4) for the outcomes using Fisher's exact conditional test with Walters normal approximation method, and assuming a power of 80% and a 2-sided α level of 0.05.

Table 9.5. Power to Detect a 3-fold Increase, by Study Outcome

Outcomes	Power Estimate
MCM	80%
Pregnancy-induced hypertension	>80%
Pre-eclampsia	>80%
Eclampsia	5.9%
Gestational diabetes	>80%
Heart failure	0%
Peripartum Cardiomyopathy	0%
Hyperemesis gravidarum	71.5%
Inadequate maternal weight gain	>80%
SAB	>80%
Stillbirth	21.4%
Induced abortion	>80%
Preterm birth	>80%
SGA	>80%
LGA	>80%
Postnatal growth deficiency	>80%
Rapid infant weight gain	>80%
Infant developmental delay	>80%

Abbreviations: MCM = major congenital malformation; SAB = spontaneous abortion; SGA = small for gestational age.

Notes: No adjustments for multiple comparisons were made. References for rates are presented in [Table 9.4](#).

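### Table 9.4 misaligns the gestational diabetes and pregnancy-induced hypertension rates with their sample sizes and misprints one heart failure figure; the powers in Table 9.5 do not rest on one cohort size

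*Protocol*

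**What the plan says.** Section 9.9.1 bases its sample sizes on "Fisher's exact conditional test with Walters normal approximation method", "assuming a power of 80%, a 2-sided α level of 0.05, an equal number of individuals in each cohort". A Table 9.4 footnote repeats the allocation: "Sampling ratio is 1:1".

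For the primary outcome, "265 live births in the analysis population of each cohort are needed to detect a 3-fold increase". This is inflated for first-trimester exposure, live birth and exclusions, 0.9 each: "364 (=265/0.9/0.9/0.9) pregnant individuals would need to be enrolled in each of the three cohorts".

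Table 9.4 is titled "Sample Size Needed per Cohort to Detect Specific Relative Risk". Its entries at issue, for RR 1.5 to 5.5, are:

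- Gestational diabetes, 6.9%: "1161 350 180 115 82 62 50 41 35".
- Pregnancy-induced hypertension, 6.5%: "1088 327 169 107 76 58 46 38 32".
- Heart failure, 0.12%: 667975 at RR 1.5, then 20706 at RR 2.0.

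Table 9.5 gives power for a threefold increase: MCM 80%, eclampsia 5.9%, stillbirth 21.4%, hyperemesis 71.5%, heart failure 0%. The text ties these to the proposed sample size. The table prints no N, and its notes name no method.

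**The concern.** Two faults in Table 9.4 can be seen without software. At a fixed relative risk, a commoner outcome needs fewer participants, yet gestational diabetes at 6.9% is shown needing more than hypertension at 6.5% in every column. Heart failure at 0.12% is shown needing more at RR 1.5 (667975) than peripartum cardiomyopathy at 0.03% (272189), which is four times rarer.

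Table 9.5 also conflicts with Table 9.4. Table 9.4 asks for 321 pregnant individuals for hyperemesis at RR 3 with 80% power. The plan expects about 364 × 0.9 = 328 in the analysis population, yet Table 9.5 prints 71.5%.

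These tables tell the reader which secondary and exploratory outcomes the registry can address. The protocol allows the sizing assumptions to be revisited after interim analyses, so the figures may be reused.

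**Working it through.** **Formula.** Walters approximation, equal groups of n, p2 = RR × p1:

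power = Φ( 2·√(n/2)·[asin√(p2 − 1/(2n)) − asin√(p1 + 1/(2n))] − 1.960 ).

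The required n is the smallest integer giving at least 0.80.

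**Reproducing the plan's own figure.** MCM: p1 = 0.03, p2 = 0.09, n = 265. The arcsine terms are 0.3014 and 0.1795, and 2·√132.5 = 23.02. The product is 2.805; less 1.960 this is 0.845, and Φ = 80.1%. The whole MCM row (2,627, 796, 413, 265, 190, 146, 117, 97, 82) reproduces exactly. Apart from the entries below, every cell of Table 9.4 reproduces to within 1. At 3.9% the method gives 201 at RR 3; 201/0.729 rounds up to 276, and 3 × 276 = 828, the alternative total in the text. The method is therefore identified.

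**Row mismatch.**

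| Rate | Sizes from the method, RR 1.5 to 5.5 | Printed beside |
|---|---|---|
| 6.5% | 1161, 350, 180, 115, 82, 62, 50, 41, 35 | gestational diabetes, 6.9% |
| 6.9% | 1088, 327, 169, 107, 76, 58, 46, 38, 32 | pregnancy-induced hypertension, 6.5% |

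All 18 cells match the other row's prevalence exactly. The gap is 73 at RR 1.5 and 8 at RR 3.

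**Heart failure, RR 1.5.** The method gives 67,975; 667975/67975 = 9.8. The other eight cells in that row match. The step from RR 1.5 to RR 2.0 confirms it: 67975/20706 = 3.28, the same as peripartum cardiomyopathy (272189/82925 = 3.28), whereas 667975/20706 = 32.

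**Table 9.5.** Candidate cohort sizes from the plan's own factors:

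- 265: first-trimester-exposed live births, after all three factors.
- 364: enrolled, before any exclusion.
- 364 × 0.9 = 327.6, about 328: analysis population.

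Power at RR 3 is shown as Walters one-tail / Walters both tails / exact Fisher:

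| Outcome (rate) | Printed | n = 265 | n = 328 | n = 364 |
|---|---|---|---|---|
| MCM (3.0%) | 80% | 80.1 / 80.1 / 80.7 | 88.6 / 88.6 / 88.5 | 91.8 / 91.8 / 91.9 |
| Hyperemesis (2.5%) | 71.5% | 70.9 / 70.9 / 71.5 | 81.1 / 81.1 / 81.2 | 85.4 / 85.4 / 85.5 |
| Stillbirth (0.596%) | 21.4% | 14.0 / 14.2 / 11.0 | 18.6 / 18.7 / 16.4 | 21.3 / 21.4 / 19.4 |
| Eclampsia (0.281%) | 5.9% | 4.7 / 5.9 / 1.3 | 6.5 / 7.3 / 2.7 | 7.5 / 8.2 / 3.7 |

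For example, hyperemesis at 328 is Φ(2.841 − 1.960) = Φ(0.881) = 81.1%.

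Hyperemesis and MCM fit 265; stillbirth fits 364. Under Walters, hyperemesis lies within 2 points of its printed value only for n of 258 to 278, and stillbirth only for about 338 to 392, so the ranges do not overlap. Yet Table 9.7 gives both outcomes the same denominator (everyone in the analysis population) and the same any-trimester exposure window. Neither printed power uses the expected size of that denominator, about 328.

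**The case against.** **Little depends on these entries.** This stands. The primary sizing reproduces. At n = 265 and RR 3, power is 99.4% at 6.5% and 99.6% at 6.9%, so both >80% entries hold whichever way the rows are corrected. Heart failure is out of reach at 67,975 as well. Only hyperemesis crosses 80%. It is exploratory, its printed power errs low, and its reference rate is itself given as a range of 0.3% to 3.5%. P-values for secondary and exploratory outcomes are nominal.

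**Table 9.5 names no method.** This also stands. The Walters statement covers the sample size calculations. The printed 0% for heart failure fits exact Fisher (0.03% at 265, 0.15% at 364) better than Walters (1.1% and 2.0%, one tail). Replacement powers must therefore be given as conditional on the method. The conflict between hyperemesis and stillbirth does not depend on that choice: at 265 stillbirth is 11–14%, and at 364 hyperemesis is about 85%.

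**Two stronger readings are tempting but unsupported.** A reader might infer three cohort sizes by solving the eclampsia power to the decimal, which gives about 308 with the one-tail formula. With both tails counted, 265 already gives 5.9%, so the plan's own two numbers, 265 and 364, account for the printed values. A reader might also conclude that the sample sizes were exchanged and the rates are right. The protocol shows only that rate and size disagree; exchanged prevalences would leave the same pattern.

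**Conclusion.** The point holds as a table correction. In Table 9.4, 18 cells do not belong to their printed prevalence, and one heart failure cell is 9.8-fold too large. Both results rest only on the stated method, which reproduces the remaining cells to within 1.

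In Table 9.5 the printed powers mix at least two cohort sizes, and two outcomes with the same denominator are treated differently. On the expected analysis population of about 328, hyperemesis power is about 81%, in line with Table 9.4's own requirement of 321, against 71.5% printed. Stillbirth power is about 16% (exact Fisher) to 19% (Walters), against 21.4% printed. These replacements assume the plan's 10% exclusion rate and general-population reference rates, and allow for no loss of effective sample size from weighting.

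The primary targets of 265 live births and 364 enrolled per cohort, and the total of 1,092, are not affected.

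**What to change.** 1. Check the gestational diabetes and pregnancy-induced hypertension prevalences against their cited sources, then make rate and sample sizes agree in both rows of Table 9.4.
2. Print 67975 for heart failure at RR 1.5.
3. Recompute Table 9.5 with one named method. For each outcome, use and print the expected N for its own denominator in Tables 9.6 and 9.7:
   - about 328 for outcomes counted in the whole analysis population, including hyperemesis and stillbirth;
   - 265 for first-trimester-exposed MCM;
   - about 295 (364 × 0.9 × 0.9 = 294.8), before further exclusions, for any-trimester live-birth outcomes;
   - a stated assumption for outcomes restricted to pregnancies of 20 weeks or more, such as eclampsia.

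A simple split into pregnancy-level and live-birth outcomes would be too coarse, because 265 carries a first-trimester factor that applies to MCM but not to outcomes such as SGA.

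The cost is a source check and a recalculation. The enrolment target, design and primary analysis do not change.

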9.9.2. Assessment of Study Feasibility

To assess the feasibility of this study, data-based assumptions regarding the prevalence of obesity, pregnancy, and tirzepatide uptake were made to estimate the number of individuals who will potentially be exposed to tirzepatide during pregnancy. The prevalence of obesity among individuals in the US, Germany, and the UK was assumed to be 39.7%, 28.8%, and 27.2%, respectively,⁸⁸⁻⁹⁰ and the proportion receiving pharmacotherapy for obesity was assumed to be 0.8%.⁹¹ It was further assumed that 15% of those receiving pharmacotherapy for obesity would be treated with tirzepatide. These assumptions were applied to the population of females of childbearing potential (aged 15–49 years) in the US, Germany, and UK (approximately 74.4 million, 42.7 million, and 14.7 million, respectively), which yielded an estimated 54,641 individuals of childbearing potential who will potentially receive tirzepatide. After application of the live birth rates (average annual number of births during a year per 1,000 persons in the population; US: 12.33/1000; Germany: 9.00/1000; UK: 8.05/1000⁹²) and the rate of pharmacotherapy discontinuation during pregnancy among individuals with obesity (95% assumed rate of discontinuation due to contraindication during pregnancy), it was estimated that 305 individuals in the US, UK, and Germany may potentially be exposed to tirzepatide during pregnancy over a 10-year period.

This estimate is less than the target sample size for the exposed cohort (364 enrolled individuals); however, this is considered a conservative estimate for several reasons. First, it is anticipated that the proportion of individuals exposed to tirzepatide will increase over the

duration of the study. Furthermore, the feasibility calculations were based on the prevalence of obesity alone, since reliable statistics regarding the prevalence of overweight and weight-related comorbidities are not available. Therefore, the estimated number of individuals with the indication could be an underestimate. Registry enrollment will be monitored, and further expansion to include additional countries will be considered as needed.

Sponsor will make best efforts to achieve its target sample size through various awareness campaign efforts (see Section 9.6.3). However, lack of motivation to participate in pregnancy registries could result in limited registry enrollment and challenges in meeting scientific objectives. To assess feasibility as outlined in the FDA Postapproval Pregnancy Safety Studies Guidance for Industry,⁴⁵ an ongoing review of registry enrollment, real world drug utilization, spontaneous pregnancy exposure reports to the company pharmacovigilance database, and external pregnancy registry publications will be performed. In conjunction with this effort, registry recruitment and awareness strategies will be evaluated to ensure that recruitment efforts reflect the size of the potential study population. If the assessment suggests that collecting sufficient information to address study objectives is infeasible, Lilly will submit a proposal to terminate additional recruitment into the pregnancy exposure registry, as a prospective registry would not be warranted.⁴⁵ If this proposal to terminate additional recruitment is submitted, follow-up will continue for the individuals already enrolled. Uptake monitoring will also continue in a US administrative claims database.

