7.4.3. Current Standard of Care

Although lifestyle modifications continue to be the first-line treatment for obesity, most people with obesity struggle to achieve and maintain weight loss with diet and exercise alone.³⁴⁻³⁹

Surgical treatments offer an effective alternative for some people with severe obesity, but bariatric surgery carries a risk in connection with the procedure and is not without post-surgical complications. Pharmacotherapy may therefore serve as a valuable adjunct to lifestyle intervention for individuals with obesity to achieve and sustain clinically relevant weight loss, improve comorbid conditions, and facilitate a healthier lifestyle.^{34,36,39}

As of 25 January 2025, a limited number of pharmacological options, including therapies with GLP-1 RA activity: semaglutide, tirzepatide, liraglutide; and non-GLP-1 RAs: orlistat, naltrexone-bupropion, setmelanotide, phentermine, phentermine-topiramate are approved for weight management in the US and the European Union (EU). All of these have shown effective weight loss, but generally only in the range of around 5% to 10% except for semaglutide and tirzepatide. The STEP 1 (NN9536-4373) trial data showed that treatment with semaglutide 2.4 mg resulted in a weight loss of up to 14.9% compared with 2.4% in the placebo group (treatment policy estimand).⁴⁰ SURMOUNT-1 (NCT04184622) data demonstrated that treatment with tirzepatide resulted in a higher weight loss of 20.9% at week 72 with 15 mg weekly doses compared with 3.1% in the placebo group (treatment regimen estimand).⁵

Additionally, since semaglutide and tirzepatide are administered once weekly, they offer a more convenient treatment option than existing weight management drugs and may improve treatment adherence.^{5,6} During pregnancy, lifestyle modifications are the primary tool for weight management.⁴¹⁻⁴³ Weight loss during pregnancy is generally discouraged and use of surgical and pharmacologic interventions are not recommended during, or immediately preceding, pregnancy due to known or suspected safety concerns as well as lack of data on safety of use during pregnancy.⁴⁴

Currently patients are advised to discontinue tirzepatide when pregnancy is recognized. However, it is expected that exposure during pregnancy may occur among real-world patients being treated for chronic weight management.

8. Research Question and Objectives

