9.5. Setting

9.5.1. Study Population

After appropriate alignment with a regulatory authority (e.g., FDA) and institutional review board (IRB)/independent ethics committee (IEC) approval of the protocol, enrollment of individuals in the registry will begin. The registry will enroll patients for up to 10 years, and the enrollment period may be extended if the target sample size is not met, and shortened if the target is met ahead of schedule.

For each enrolled pregnant individual, participation will begin at the time of providing informed consent and end either at pregnancy outcome (if fetal loss – SAB, stillbirth, or induced abortion) or 12 months after pregnancy outcome (if live birth). For each live born infant of prospectively enrolled participants, infant follow-up will begin at birth and end at 12 months of age. For each live born infant of retrospectively enrolled participants, infant follow-up will begin at the time of enrollment and end at 12 months of age; data will be collected retrospectively from time of enrollment to birth outcome. Maternal and fetal outcomes will be assessed through the end of pregnancy, and infant outcomes will be assessed through 12 months of infant age. However, pregnancy outcomes prior to first contact with the Virtual Registry Coordination Center (VRCC) (i.e., retrospectively enrolled participants) will be excluded in the main analysis (Section 9.5.2).

The study population will include three cohorts of pregnant individuals:

- Tirzepatide exposed cohort: A cohort of individuals who are treated with tirzepatide for weight management during pregnancy.
- Anti-obesity medication (AOM) active comparator cohort: A cohort of individuals who are treated with pharmacotherapy other than tirzepatide or other therapies with GLP-1 RA activity for weight management during pregnancy. The comparator AOMs may include, but not limited to, orlistat, setmelanotide, and naltrexone-bupropion.
- AOM unexposed comparator cohort: A cohort of individuals who have obesity or are overweight in the presence of at least one weight-related comorbid condition at the time of conception; and who are not treated with tirzepatide, GLP-1 RA therapies, or any products for weight management during pregnancy.

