9.6.3.2. Retention Strategy

A retention strategy, facilitated by engaging both the participant and HCP, will seek to minimize the reporting burden on these groups to the extent possible.

The registry staff will serve as the first and single point of communication for both registry participants and HCPs. The specialized staff, many of whom are obstetric nurses, have experience collecting data for observational studies from both patients and research naïve HCPs. They are experts at developing a rapport with HCPs and participants to facilitate data collection and build one-on-one relationships that will promote retention and reduce overall loss to follow up. To promote HCP engagement, status updates may be shared with HCPs through various means (i.e., email, newsletters, and the registry website). Materials provided will emphasize the mission of the registry to promote participant engagement and point participants to the website.

The registry will use streamlined data collection processes and simple, concise data collection forms that focus on specified outcomes to reduce the burden of reporting. The registry will provide multiple options for communication and data submission (e.g., phone, fax, mail, email,

website, web based/mobile application) and a flexible follow-up schedule to enhance retention and maximize data reporting. The registry will also attempt to collect contact information of family members or friends in case the participant cannot be reached, which can further promote retention. Finally, in countries where local guidelines permit, the registry will provide stipends to participants (at enrollment and at the end of data collection) and their HCPs who serve as data reporters (once all data have been collected and all queries have been resolved).

Assessment of Recruitment and Retention

Participant recruitment and retention are the greatest challenges experienced with pregnancy registries. Recruitment largely depends on a strong awareness campaign and product use or uptake in the market. It is important to note that low recruitment/enrollment in pregnancy registries may be due to limited use of the product, especially when the product is new to the market. Pregnancy registries typically enroll only a small fraction of all exposed pregnancies, regardless of awareness strategies employed.

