9.6.4. Participant Registration

Pregnant individuals who are interested in providing data to the registry and participating in the registry may self-enroll through the web-based application or by calling the VRCC. To enroll, each individual will answer a series of screening questions to assess their eligibility, and, if eligible, they will be asked to provide informed consent, their primary contact information, alternate contact information for a family member or friend, contact information for HCPs who are/will be involved in their care or the care of their infant, and medical releases to allow these HCPs to provide data to the registry. To allow for full follow-up on all enrolled pregnant individuals and their infants prior to study end, the last participant will be enrolled on or before 31 December 2033.

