DOC, defined as 2^{0/7} gestational weeks, will be calculated as first day of LMP plus 14 days (2 weeks).

If EDD is not reported by the HCP but LMP data are available, the registry will use first day of LMP to calculate EDD, gestational age, and DOC.

Individuals will be considered exposed during pregnancy if the exposure occurs any time from 25 days prior to the DOC to the pregnancy outcome. For the analysis of MCM, first trimester exposure will be defined as exposure from 5 times the product's half-life (i.e., 25 days for tirzepatide) prior to the DOC to 13^{6/7} gestational weeks.

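### The feasibility figure of 305 exposed pregnancies uses a whole-population birth rate on women aged 15–49, removes women the protocol counts as exposed, and covers 10 years where the dates give 8.26

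*Protocol*

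**What the plan says.** Section 9.9.2 builds its estimate in steps. "The prevalence of obesity among individuals in the US, Germany, and the UK was assumed to be 39.7%, 28.8%, and 27.2%, respectively". Of these individuals 0.8% are taken to receive obesity drugs, and 15% of those to receive tirzepatide. The shares are applied to 74.4, 42.7 and 14.7 million females aged 15–49 in the US, Germany and the UK, giving 54,641 potential users. The text continues: "After application of the live birth rates (average annual number of births during a year per 1,000 persons in the population", with rates of 12.33, 9.00 and 8.05 per 1,000. A further reduction follows: "95% assumed rate of discontinuation due to contraindication during pregnancy". The result is 305 over 10 years. The section notes that this is below 364 but calls it conservative, because uptake may rise and overweight patients are not counted.

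Other sections bear on these inputs:

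- Section 9.7.5: "Individuals will be considered exposed during pregnancy if the exposure occurs any time from 25 days prior to the DOC to the pregnancy outcome".
- Section 7.4.3: "Currently patients are advised to discontinue tirzepatide when pregnancy is recognized".
- Section 9.5.1: "The registry will enroll patients for up to 10 years", with extension allowed if the target is not met.
- Section 6 starts data collection on 28 September 2025 and ends it on 30 June 2035.
- Section 9.6.4, in order to allow full follow-up: "the last participant will be enrolled on or before 31 December 2033".
- Section 9.6.3.2: "Pregnancy registries typically enroll only a small fraction of all exposed pregnancies, regardless of awareness strategies employed".

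**The concern.** Four inputs do not fit the quantity being estimated. The birth rate has all persons in its denominator, but it multiplies women aged 15–49 only. The 95% reduction is for stopping during pregnancy, yet a woman who stops after conceiving on the drug has already met the exposure definition. The 10-year span is longer than the planned enrollment dates. The result counts women who might be exposed, whereas 364 counts women who enroll.

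This is the only numerical feasibility estimate in the protocol. A reader who takes it at face value would conclude that the exposed cohort cannot be filled even if every exposed woman joined. With the inputs corrected, the question becomes what share of a much larger pool will take part.

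A related date problem affects follow-up. Section 9.6.4 presents 31 December 2033 as late enough to close enrollment and still complete follow-up, and this is not so for women enrolled early in pregnancy.

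**Working it through.** **Reproducing 305.** Users = females 15–49 × obesity prevalence × 0.008 × 0.15.

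| | Users | Birth rate | Births/year |
|---|---|---|---|
| US | 74.4M × 0.397 × 0.0012 = 35,444 | 0.01233 | 437.0 |
| Germany | 42.7M × 0.288 × 0.0012 = 14,757 | 0.00900 | 132.8 |
| UK | 14.7M × 0.272 × 0.0012 = 4,798 | 0.00805 | 38.6 |
| Total | 54,999 (stated 54,641) | | 608.5 |

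608.5 × 10 years = 6,085, and × 0.05 = 304 (stated 305). The match shows that the per-person rate, 5% retention and a full 10 years were used.

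**Birth-rate denominator.** If women aged 15–49 are a share *f* of the population, the rate per woman is the stated rate divided by *f*. The protocol does not give *f*. For *f* = 0.30 to 0.20 (assumed), the factor is 3.3 to 5.0, so 304 becomes 1,014 to 1,521 over 10 years.

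**Discontinuation.** Let *p* be the share of these women who stop more than 25 days before conception. The count is 6,085 × (1 − *p*). The plan's 304 is right only if *p* = 0.95, that is, if all the assumed discontinuation happens before the exposure window. At *p* = 0 it is 6,085, the upper bound. At *p* = 0.5 it is 3,042.

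**Time span.** 28 September 2025 to 31 December 2033 is 8.26 years. 608.5 × 8.26 × 0.05 = 251.

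**Participation needed for 364 over 8.26 years.**

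- Plan's other inputs: 364/251 = 145%, which is impossible.
- Denominator corrected: pool 837 to 1,256, so 43% to 29%.
- 95% cut also removed: pool 16,748 to 25,122 (upper bounds), so 2.2% to 1.4%.

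**German input.** 42.7/14.7 = 2.9 times the UK figure. Germany supplies 132.8/608.5 = 22% of births. Dropping Germany altogether leaves (437.0 + 38.6) × 10 × 0.05 = 238, so an error in that input could lower 304 to no less than 238.

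**Follow-up date.** A 12-month assessment by 30 June 2035 needs birth by 30 June 2034, which is 181 days or 25.9 weeks after 31 December 2033. For a birth at 40 weeks, gestation at enrollment must be at least 40 − 25.9 = 14.1 weeks. Section 9.11.2.2 allows ±2 weeks around 12 months, which lowers this to about 12.1 weeks. A woman enrolled that day at 8 weeks is due on 12 August 2034, and her infant reaches 12 months 43 days after data collection ends.

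**The case against.** The strongest reply is that 305 does no work. It does not enter the 364 target, the power table or any analysis. A reader might infer that it governs adding countries or proposing to stop recruitment. The text does not support that: expansion follows monitored enrollment (Sections 9.1 and 9.9.2), and a proposal to stop follows ongoing review of enrollment, drug utilization, spontaneous reports and outside registry publications (Section 9.9.2). This stands and limits the consequence.

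A reader might also infer that calling 305 conservative is simply wrong. As a count of exposed pregnancies it is low, so the word is right in direction, though not for the reasons given. It does not carry over to the comparison with enrolled women.

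The 95% figure could include women who stop before conceiving. Section 7.4.3 also says drug treatment is not recommended just before pregnancy, and no section gives the timing of discontinuation. Hence the 20-fold effect is only an upper bound. Still, the reduction is worded as discontinuation during pregnancy, and Section 9.9.1 assumes that 90% of enrollees are exposed in the first trimester.

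The 10-year span agrees with Section 9.5.1, which permits extension, so that item is a conflict between sections worth 17%. Section 9.9.2 does not say that every exposed woman will enroll, and low participation is disclosed elsewhere. What remains is that 305 and 364 are compared without a participation rate. The absence of a similar estimate for the active comparator cohort is a gap one might like filled, not an error.

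On follow-up, few women are affected. At 364/8.26 = 44 per year, the last 8 weeks bring about 7 enrollees per cohort, and only those early in gestation lose the 12-month assessment. Their birth and 4-month data are kept.

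**Conclusion.** The point holds as an error in a stated feasibility figure. That the birth rate understates births is certain; the 3.3 to 5 fold size rests on an assumed 20–30% share of women aged 15–49, applied alike to three countries. The 95% cut conflicts with the protocol's own exposure definition; removing it raises 304 to at most about 6,085 over 10 years, less whatever share of women truly stop before the 25-day window. The shorter enrollment span works the other way, from 304 to 251. The net effect is a large understatement of exposed pregnancies.

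This does not show that recruitment will be easy. The larger counts are pools of potentially exposed live-birth pregnancies, not expected enrollment, and the protocol itself expects only a small fraction to join. It shows that 305 cannot support a feasibility conclusion in either direction.

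The last-enrollment date does not secure full follow-up for women enrolled on 31 December 2033 before about 14 weeks (about 12 with the assessment window) who deliver at term.

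**What to change.** Recompute Section 9.9.2:

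1. Use births, or pregnancies, per 1,000 women aged 15–49. Pregnancies would also cover fetal losses, which the registry enrolls: at the plan's 90% live-birth rate, 304/0.9 = 338.
2. Check the German input of 42.7 million against its source.
3. Apply discontinuation only to women who stop before the 25-day window, with the assumed share shown as a range.
4. Use 8.26 years, or reconcile Sections 9.5.1 and 9.9.2 with Section 9.6.4.
5. Multiply by a participation rate shown as a range before comparing with 364.

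Separately, reconcile Section 9.6.4 with the 30 June 2035 end of data collection. One option is to limit late enrollment by estimated date of delivery: about mid-June 2034 leaves room for the full ±2-week window, and end-June 2034 is the latest that reaches 12 months. The other is to move the end of data collection to about end-September 2035. A woman enrolled at 4 weeks on 31 December 2033 is due on 9 September 2034, so her infant's 12-month window closes on 23 September 2035. The June 2036 report date can stand.

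The cost is one recalculated paragraph and one changed date. No participants are added and no analysis changes. A few late enrollees per cohort are lost, or one milestone moves.
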